### 10.3.4 Safety Analyses

Safety endpoints will be analyzed as summary statistics during treatment. Adverse events will be PI reported. Adverse events leading to premature discontinuation from the study will be presented in a table.

### 10.3.5 Adherence and Retention Analyses

Not applicable.

### 10.3.6 Baseline Descriptive Statistics

Not applicable. Each patient will serve as an internal control.

### 10.3.7 Tabulation of Individual Response Data

Individual participant data will be listed by measure and time point.

### 10.3.8 Exploratory Analyses

Not applicable.

### 10.4 Sample Size

34 participants will be recruited to meet a goal of evaluable participants for the study.

- Outcome measure: diagnostic accuracy
- Test statistic: descriptive statistics

Study number: i20-00356 Page 25 Version: June 8, 2020

• Null hypothesis: We hypothesize that there will be no difference in the diagnostic accuracy of the Arthrex NanoScope compared to conventional arthroscopic instruments.

• Type I error rate (alpha): 0.95

Power level: 0.819

Dropout: Not applicable.

• Approach to handling withdrawals and protocol violations: Not applicable.

Statistical method used to calculate the sample size: At 90% prevalence, in order to detect a change in sensitivity (true-positive) between .70 (sensitivity of MRI) and .90 (sensitivity of arthroscopy), we would need a minimum of 34 subjects with a minimum of 31 who had a ligamentous wrist injury (see table below). This was determine with the guidance of the Center for Clinical Research.

Mohamad Adam Bujang and Tassha Hilda Adnan, Requirements for Minimum Sample Size for Sensitivity and Specificity Analysis

www.jcdr.net

H a 0.60 0.70 0.80 0.90 0.70 0.80 0.90 0.90 0.90 0.90 0.95 0.60 0.70 0.80	Power 0.804 0.810 0.804 0.889 0.801 0.826 0.885 0.818 0.807 0.819 0.816 0.804 0.804	p-value 0.047 0.044 0.041 0.039 0.048 0.034 0.035 0.044 0.048 0.040 0.048	N1 199 49 20 12 181 45 19 155 31 107 231 199	N 284 70 29 17 259 64 27 221 44 153 330		Perv 70% 70% 70% 70% 70% 70% 70% 70% 70% 70%	H o 0.50 0.50 0.50 0.50 0.60 0.60 0.60 0.70	H a 0.60 0.70 0.80 0.90 0.70 0.80 0.90 0.80 0.90	0.804 0.810 0.804 0.889 0.801 0.826 0.885 0.818	p-value 0.047 0.044 0.041 0.039 0.048 0.034 0.035 0.044	N1 464 114 47 28 422 105 44 362	N 663 163 67 40 603 150 63 517
0.70 0.80 0.90 0.70 0.80 0.90 0.90 0.90 0.95 0.60	0.810 0.804 0.889 0.801 0.826 0.885 0.818 0.807 0.819 0.816 0.804 0.804	0.044 0.041 0.039 0.048 0.034 0.035 0.044 0.048 0.040 0.048 0.047	49 20 12 181 45 19 155 31 107 231	70 29 17 259 64 27 221 44 153 330		70% 70% 70% 70% 70% 70% 70% 70%	0.50 0.50 0.50 0.60 0.60 0.60 0.70	0.70 0.80 0.90 0.70 0.80 0.90	0.810 0.804 0.889 0.801 0.826 0.885 0.818	0.044 0.041 0.039 0.048 0.034 0.035	114 47 28 422 105 44 362	163 67 40 603 150 63
0.80 0.90 0.70 0.80 0.90 0.80 0.90 0.90 0.96 0.60	0.804 0.889 0.801 0.826 0.885 0.818 0.807 0.819 0.816 0.804	0.041 0.039 0.048 0.034 0.035 0.044 0.048 0.040 0.048 0.047	20 12 181 45 19 155 31 107 231	29 17 259 64 27 221 44 153 330		70% 70% 70% 70% 70% 70% 70%	0.50 0.50 0.60 0.60 0.60 0.70	0.80 0.90 0.70 0.80 0.90	0.804 0.889 0.801 0.826 0.885 0.818	0.041 0.039 0.048 0.034 0.035 0.044	47 28 422 105 44 362	67 40 603 150 63
0.90 0.70 0.80 0.90 0.80 0.90 0.90 0.90 0.95 0.60	0.889 0.801 0.826 0.885 0.818 0.807 0.819 0.816 0.804 0.804	0.039 0.048 0.034 0.035 0.044 0.048 0.040 0.047	12 181 45 19 155 31 107 231	17 259 64 27 221 44 153 330		70% 70% 70% 70% 70% 70%	0.50 0.60 0.60 0.60 0.70	0.90 0.70 0.80 0.90 0.80	0.889 0.801 0.826 0.885 0.818	0.039 0.048 0.034 0.035 0.044	28 422 105 44 362	40 603 150 63
0.70 0.80 0.90 0.80 0.90 0.90 0.90 0.95 0.60 0.70	0.801 0.826 0.885 0.818 0.807 0.819 0.816 0.804 0.810	0.048 0.034 0.035 0.044 0.048 0.040 0.048 0.047	181 45 19 155 31 107 231	259 64 27 221 44 153 330		70% 70% 70% 70% 70%	0.60 0.60 0.60 0.70	0.70 0.80 0.90 0.80	0.801 0.826 0.885 0.818	0.048 0.034 0.035 0.044	422 105 44 362	603 150 63
0.80 0.90 0.80 0.90 0.90 0.95 0.60 0.70	0.826 0.885 0.818 0.807 0.819 0.816 0.804 0.810	0.034 0.035 0.044 0.048 0.040 0.048 0.047 0.044	45 19 155 31 107 231	64 27 221 44 153 330		70% 70% 70% 70%	0.60 0.60 0.70	0.80 0.90 0.80	0.826 0.885 0.818	0.034 0.035 0.044	105 44 362	150
0.90 0.80 0.90 0.90 0.95 0.60 0.70	0.885 0.818 0.807 0.819 0.816 0.804 0.810	0.035 0.044 0.048 0.040 0.048 0.047 0.044	19 155 31 107 231	27 221 44 153 330		70% 70% 70%	0.60	0.90	0.885	0.035	44 362	63
0.80 0.90 0.90 0.95 0.60 0.70	0.818 0.807 0.819 0.816 0.804 0.810	0.044 0.048 0.040 0.048 0.047 0.044	155 31 107 231	221 44 153 330		70% 70%	0.70	0.80	0.818	0.044	362	
0.90 0.90 0.95 0.60 0.70 0.80	0.807 0.819 0.816 0.804 0.810 0.804	0.048 0.040 0.048 0.047 0.044	31 107 231	44 153 330		70%			Notice and the second			517
0.90 0.95 0.60 0.70 0.80	0.819 0.816 0.804 0.810 0.804	0.040 0.048 0.047 0.044	107 231	153 330		202-204	0.70	0.90	0.807	0.040		
0.95 0.60 0.70 0.80	0.816 0.804 0.810 0.804	0.048 0.047 0.044	231	330		70%				0.048	72	100
0.60 0.70 0.80	0.804 0.810 0.804	0.047				1 M. CM	0.80	0.90	0.819	0.040	250	357
0.70	0.810	0.044	199			70%	0.90	0.95	0.816	0.048	539	770
0.80	0.804			249		80%	0.50	0.60	0.804	0.047	796	998
			49	61		80%	0.50	0.70	0.810	0.044	196	24
0.90	0.889	0.041	20	25		80%	0.50	0.80	0.804	0.041	80	10
		0.039	12	15		80%	0.50	0.90	0.889	0.039	48	60
0.70	0.801	0.048	181	226		80%	0.60	0.70	0.801	0.048	724	90
0.80	0.826	0.034	45	56		80%	0.60	0.80	0.826	0.034	180	22
0.90	0.885	0.035	19	24		80%	0.60	0.90	0.885	0.035	76	95
0.80	0.818	0.044	155	194		80%	0.70	0.80	0.818	0.044	620	77
0.90	0.807	0.048	31	39		80%	0.70	0.90	0.807	0.048	124	15
0.90	0.819	0.040	107	134		80%	0.80	0.90	0.819	0.040	428	53
0.95	0.816	0.048	231	289		80%	0.90	0.95	0.816	0.048	924	115
0.60	0.804	0.047	199	221		90%	0.50	0.60	0.804	0.047	1791	199
0.70	0.810	0.044	49	54		90%	0.50	0.70	0.810	0.044	441	49
0.80	0.804	0.041	20	22		90%	0.50	0.80	0.804	0.041	180	20
0.90	0.889	0.039	12	13		90%	0.50	0.90	0.889	0.039	108	12
0.70	0.801	0.048	181	201		90%	0.60	0.70	0.801	0.048	1629	181
0.80	0.826	0.034	45	50		90%	0.60	0.80	0.826	0.034	405	45
0.90	0.885	0.035	19	21		90%	0.60	0.90	0.885	0.035	171	19
0.80	0.818	0.044	155	172		90%	0.70	0.80	0.818	0.044	1395	158
0.90	0.807	0.048	31	34		90%	0.70	0.90	0.807	0.048	279	31
0.90	0.819	0.040	107	119		90%	0.80	0.90	0.819	0.040	963	107
	0.816	0.048	231	257		90%	0.90	0.95	0.816	0.048	2079	231
	0.80 0.90 0.80 0.90 0.90	0.80 0.826 0.90 0.885 0.80 0.818 0.90 0.807 0.90 0.819 0.95 0.816 de calculation for set	0.80 0.826 0.034 0.90 0.885 0.035 0.80 0.818 0.044 0.90 0.807 0.048 0.90 0.819 0.040 0.95 0.816 0.048	0.80	0.80	0.80	0.80	0.80	0.80	0.80	0.80	0.80

CONFIDENTIAL

This material is the property of the NYU School of Medicine and Langone Medical Center. Do not disclose or use except as authorized in writing by the study sponsor Interventional Template Version: 11 January 2019

Version: June 8, 2020

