### 5.6 Total Number of Participants and Sites

Recruitment will end when approximately 34 participants are enrolled. It is expected that approximately 34 participants will be enrolled in order to produce 34 evaluable participants. Participants will be enrolled at four 4 NYU study sites:

- 1. NYU Langone Orthopedic Hospital
- 2. Tisch Hospital, NYU Langone Health
- 3. NYU Langone Orthopedic Center (38th Street)
- 4. Joan H. & Preston Robert Tisch Center at Essex Crossing, NYU Langone Health

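### Section 10.4 states an alpha of 0.95 and a power of 0.819; its own table gives 0.807 at about 0.05, and 34 enrolled at 90% prevalence gives about 73% power

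*Combined protocol and SAP*

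**What the plan says.** Section 10.4 (Sample Size) gives "Type I error rate (alpha): 0.95" and "Power level: 0.819". The design is described as "At 90% prevalence, in order to detect a change in sensitivity (true-positive) between .70 (sensitivity of MRI) and .90 (sensitivity of arthroscopy"), from which it concludes that "we would need a minimum of 34 subjects with a minimum of 31 who had a ligamentous wrist injury". Dropout is marked as not applicable.

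The published table reproduced below that text has two rows that matter, both at 90% prevalence. After the null sensitivity, the columns are the alternative sensitivity, power, p-value, number with the condition (N1) and total number (N):

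- 0.70 versus 0.90: "0.90 0.807 0.048 31 34"
- 0.80 versus 0.90: "0.90 0.819 0.040 107 119"

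Section 10.3.1 and the Protocol Summary set significance at p < .05. Section 5.6 stops recruitment at about 34 and adds: "It is expected that approximately 34 participants will be enrolled in order to produce 34 evaluable participants". No rule keeps recruitment open until 31 injured wrists have been seen.

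**The concern.** Alpha and power are the two numbers offered to justify the size of the study, and both disagree with the table cited as their source. The alpha looks like a confidence level (1 − 0.05) entered in the wrong field. The power looks like a value read from the neighbouring row.

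There is a further problem beyond transcription. The table's power assumes a fixed number of injured wrists, but the plan fixes the number enrolled, so the number injured is left to chance. The expected number is already below the stated minimum of 31. Section 10.1 says that a formal SAP is still to be written, so uncorrected figures could be carried into it.

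**Working it through.** **Inputs.** Null sensitivity 0.70, alternative 0.90, prevalence 0.90, N = 34 and N1 = 31 (Section 10.4); significance level 0.05 (Section 10.3.1). Section 10.4 does not name the test or its sidedness. I used a one-sample exact binomial test with at most 0.025 in each tail, because it reproduces the power and p-value of all 11 distinct rows of the sensitivity table to three decimals.

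**The plan's two rows.** For n injured wrists, reject when the number detected is at least u or at most l, the widest limits with P(X ≥ u) ≤ 0.025 and P(X ≤ l) ≤ 0.025 under the null. Power is the probability of rejection under the alternative.

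| Row | Reject if | Attained alpha | Power | Table |
|---|---|---|---|---|
| 0.70 vs 0.90, n = 31 | ≥ 27 or ≤ 16 | 0.0478 | 0.8068 | 0.048 / 0.807 |
| 0.80 vs 0.90, n = 107 | ≥ 94 or ≤ 76 | 0.0402 | 0.8191 | 0.040 / 0.819 |

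The stated 0.819 is therefore the power of the second design, whose total of 119 is 119/34 = 3.5 times the planned enrolment. Other tests at n = 31 do not give 0.819 either: one-sided exact at 0.05 or 0.025 gives 0.807, and the normal approximation gives 0.764 two-sided and 0.885 one-sided.

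**The stated alpha.** Taken literally, 0.95 in the same test at n = 31 gives an attained type I error of about 0.84 and a power of 0.998. It cannot be paired with 0.819.

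**From 31 injured to 34 enrolled.** 31/0.90 = 34.4, which the table shows as 34. In the other direction, 34 × 0.90 = 30.6. With D, the number injured, distributed as Binomial(34, 0.90), P(D ≥ 31) = 0.554.

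**Power by number injured, and its average.** Exact power moves in a saw-tooth, and 31 is a local peak.

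| Injured d | P(D = d) | Power at d | Product |
|---|---|---|---|
| ≤ 27 | 0.0481 | – | 0.0312 |
| 28 | 0.0704 | 0.695 | 0.0489 |
| 29 | 0.1311 | 0.671 | 0.0879 |
| 30 | 0.1966 | 0.647 | 0.1273 |
| 31 | 0.2283 | 0.807 | 0.1842 |
| 32 | 0.1926 | 0.789 | 0.1519 |
| 33 | 0.1051 | 0.770 | 0.0809 |
| 34 | 0.0278 | 0.750 | 0.0209 |

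The products sum to 0.733.

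**Sensitivity to prevalence.** The documents give no source for 90%. The other values below are assumptions.

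| Prevalence | P(D ≥ 31) | Average power |
|---|---|---|
| 80% | 0.07 | 0.640 |
| 85% | 0.23 | 0.687 |
| 90% | 0.55 | 0.733 |
| 95% | 0.91 | 0.767 |

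**Sensitivity to the test, at 90% prevalence.** Average power is 0.755 with a two-sided normal approximation, 0.768 with a minimum-likelihood two-sided exact test, and 0.822 with a one-sided exact test at 0.05. The one-sided test is not the one behind the table: its attained alpha at n = 31 is 0.024, not 0.048.

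**The case against.** The best defence is that these are two clerical slips. The sample size was read from the correct row, so correcting alpha and power leaves 34 unchanged. No analysis would be run at 0.95, so the 84% error rate describes a test nobody proposes. The power slip is 0.819 − 0.807 = 1.2 points, and both values exceed 0.80. The primary analysis in Section 10.3.2 is a descriptive percentage, so no decision rule depends on these figures. All of that is fair, but Section 10.4 still offers alpha and power as the reason for 34, and they contradict its own table.

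The 73% is open to more challenge. It depends on a test the section does not name and on treating the number injured as random. Section 10.4 can also be read as setting 31 as a requirement rather than predicting it. Given at least 31 injured, average power is about 0.79. The Protocol Summary describes wrists in which examination and imaging have already confirmed internal damage, which makes a high prevalence plausible; at 95% the average is 0.767. These points call for stating the assumptions. They do not restore the stated figure: every two-sided variant at 90% prevalence stays between 0.73 and 0.77, and Section 5.6 has no rule that secures 31.

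The missing dropout allowance is a minor matter, since participation lasts one day with no follow-up. It is not zero, because Section 7.2.5 allows withdrawal before the procedure and Section 8.4.1 has data destroyed if a participant cannot continue.

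**Conclusion.** The concern holds. The alpha of 0.95 is an error; the plan's level is 0.05, attained as 0.048 at 31 injured wrists. The power of 0.819 belongs to another row; the correct value for the row used is 0.807, and only with exactly 31 injured wrists. These two findings follow from the plan's own table and need no outside assumption.

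For the study as it will be run, with enrolment stopping at about 34, expected power is about 73%, or 81.9 − 73.3 = 8.6 points below the stated figure. That rests on 90% prevalence, a binomial number of injured wrists, and the equal-tailed exact test that generates the table. It is 69% at 85% prevalence and 64% at 80%.

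**What to change.** In Section 10.4:

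1. Set alpha to 0.05, two-sided, and name the exact binomial test, so that the entry listing only descriptive statistics no longer conflicts with a power calculation.
2. Replace 0.819 with 0.807, stated as conditional on exactly 31 injured wrists.
3. State that 34 enrolled at 90% prevalence gives an expected 30.6 injured, a 55% chance of at least 31, and an expected power of about 73%, with 69% at 85% prevalence and 64% at 80%. Give the source of the 90%, or label it as an assumption.
4. Make clear that 34 enrolled does not by itself secure the minimum of 31.

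This is a wording change in one section. It needs no added patients or procedures. Its cost is a less favourable stated power. If the sponsor prefers to keep 80% expected power, the same method at 90% prevalence needs about 40 enrolled (0.792 at 39, 0.806 at 40); that is a separate decision.

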### 3.2 Secondary Objectives (if applicable)

To determine if the diagnostic accuracy of the Arthrex NanoScope compared to conventional arthroscopic instruments results in a change in intended intervention.

To determine the surgeon-rated ease of use and diagnostic confidence of the Arthrex NanoScope.

To determine the diagnostic correlation between pre-operative MRI and arthroscopy (NanoScope and conventional). The MRI is standard of care for evaluation of ligamentous wrist pathology. It will not be mandated as part of the protocol.

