### 10 Statistical Considerations

### 10.1 Statistical and Analytical Plans (SAP)

A formal SAP will be completed prior to database lock.

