# 10.2 Statistical Hypotheses

We hypothesize that there will be no difference in the diagnostic accuracy of the Arthrex NanoScope compared to conventional arthroscopic instruments.

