### 10.3 Description of Statistical Methods

### 10.3.1 General Approach

Descriptive statistics will be used to provide a quantitative summary of the data in the study. Specifically, the analysis performed included measures of central tendency (mean, median, and mode) and measures of variability (range and standard deviation). Categorical data will be described in percentages and a Chi-squared test will be employed to detect if these categorical variables are related between the two treatment groups with a p value of < .05. Continuous data will be described in means with standard deviations. A two -tailed Student's T-test will be employed to compare the means between the two treatment groups with a p value of < .05.

Version: June 8, 2020

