### 10.3.2 Analysis of the Primary Efficacy Endpoint(s)

### **Primary**

1. Diagnostic accuracy of Nanoscope compared to conventional arthroscope.

Diagnostic accuracy of the Arthrex Nanoscope will be described as a incidence/percentage compared to the diagnosis determined by wrist arthroscopy with conventional instruments.

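### The power in section 10.4 belongs to no planned test: N=34 was sized on sensitivity 0.70 versus 0.90, the stated null and analysis concern something else, and 0.819 is another row's figure

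*Combined protocol and SAP*

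**What the plan says.** **Sizing (10.4).** At 90% prevalence, 34 subjects with at least 31 injured are required "in order to detect a change in sensitivity (true-positive) between .70 (sensitivity of MRI) and .90 (sensitivity of arthroscopy"). The same section lists "Test statistic: descriptive statistics" and "Power level: 0.819", and prints the type I error rate as 0.95. It reproduces a published sample-size table. At 90% prevalence, the sensitivity side of that table reads:

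- 0.70 versus 0.90: power 0.807, p-value 0.048, 31 injured, 34 in total.
- 0.80 versus 0.90: power 0.819, p-value 0.040, 107 injured, 119 in total.

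**Hypothesis (10.2, repeated in 10.4 as the null).** "We hypothesize that there will be no difference in the diagnostic accuracy of the Arthrex NanoScope compared to conventional arthroscopic instruments".

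**Primary analysis (10.3.2).** "Diagnostic accuracy of the Arthrex Nanoscope will be described as a incidence/percentage compared to the diagnosis determined by wrist arthroscopy with conventional instruments".

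**General methods (10.3.1).** For categorical data, "a Chi-squared test will be employed to detect if these categorical variables are related between the two treatment groups", at p < .05.

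**Related text.** The objectives in the Protocol Summary and the final assessments in the study schematic name sensitivity and specificity, with conventional arthroscopy as the reference. Section 4.2.1 says the primary endpoint was chosen to judge whether the smaller scope can be used alone. MRI enters only through a secondary correlation (10.3.3), in patients who have a radiology report (7.1.1). Of the MRI, section 3.2 says "It will not be mandated as part of the protocol". Section 10.1 adds: "A formal SAP will be completed prior to database lock".

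**The concern.** Sample size, hypothesis and analysis should describe one comparison. Here the sizing tests a sensitivity against an MRI benchmark, the hypothesis concerns conventional arthroscopy, and the analysis is a descriptive percentage. Section 10.4 does not say which instrument, or which reference, the 0.90 refers to.

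A reader who meets a null of no difference beside a power of 0.819 will take that power as support for a finding of no difference. It gives none. Even if the 0.70 test were run and rejected, it would show only that sensitivity exceeds 0.70. The aim in 4.2.1 turns on how low the accuracy could plausibly be, and the plan provides no interval from which to read that.

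**Working it through.** **Inputs, all from 10.4 and its table.** Null sensitivity 0.70; alternative 0.90; 31 injured wrists; prevalence 90%; stated power 0.819. Alpha is printed as 0.95. I took 0.05 two-sided, because 10.3.1 uses p < .05 and every p-value in the table is below 0.05.

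**1. Reproduce the plan's N.** For X ~ Bin(n, p), reject if X ≥ b or X ≤ a, with each tail at most 0.025 under the null.

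- n = 31, null 0.70: b = 27 and a = 16.
- Size = P(X ≥ 27) + P(X ≤ 16) at 0.70 = 0.0239 + 0.0239 = 0.0478. The table prints 0.048.
- Power at 0.90 = P(X ≥ 27) = 0.8068, with a negligible lower tail. The table prints 0.807.
- 31 is the smallest n that reaches power 0.80 under this test.
- Total N = 31 / 0.90 = 34.4, printed as 34.

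So N = 34 is the one-sample 0.70 versus 0.90 design.

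**2. Find where 0.819 comes from.**

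- n = 107, null 0.80, alternative 0.90: reject at ≥ 94 or ≤ 76; size 0.0402; power 0.8191. The table prints 0.040 and 0.819.
- Total = 107 / 0.90 = 118.9, printed as 119.
- Other methods at n = 31 for 0.70 versus 0.90: normal approximation 0.764 two-sided and 0.885 one-sided; exact one-sided 0.807. None gives 0.819.

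The same exact method matches six further rows of the table to three decimals. The printed power therefore matches the 0.80 versus 0.90 row. That it was copied from there is an inference. The difference is 0.819 − 0.807 = 0.012.

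**3. Look for the sized test among the planned analyses.**

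| Place | Quantity | Compared with | Test |
|---|---|---|---|
| 10.4, sizing | sensitivity | 0.70, labelled MRI | exact one-sample |
| 10.2 and 10.4, null | accuracy | conventional arthroscopy | none named |
| 10.3.2 | accuracy, as a percentage | conventional arthroscopy as reference | none |
| 10.3.1 | categorical data in general | two groups | unpaired chi-squared |
| 10.3.3 | MRI correlation | arthroscopy | none; percentages |

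No planned analysis is the test in the first row. The chi-squared is generic and not tied to the primary endpoint. It treats the two scopes as separate groups, whereas each wrist is examined with both and one scope is the reference standard.

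**4. What 34 patients support for the planned percentages.** Exact (Clopper-Pearson) 95% limits for x out of n, assuming one result per wrist: lower = the 0.025 quantile of Beta(x, n − x + 1); upper = the 0.975 quantile of Beta(x + 1, n − x). When x = n the lower limit is 0.025^(1/n).

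- Accuracy 31/34 (91.2%): 76.3% to 98.1%.
- Sensitivity 28/31 (90.3%): 74.2% to 98.0%.
- Specificity: 34 × 0.10 = 3.4 uninjured wrists expected. For 3/3 the lower limit is 0.025^(1/3) = 29.2%.
- Ceilings with perfect agreement: sensitivity 31/31, 0.025^(1/31) = 88.8%; accuracy 34/34, 0.025^(1/34) = 89.7%.

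**The case against.** The best defence is that this is a small descriptive study. Section 10.4 names descriptive statistics, 10.3.2 plans a percentage, and no decision uses the power. Sensitivity against conventional arthroscopy is a named outcome, so sizing from a sensitivity table with 0.70 as a lower benchmark is plausible, if poorly explained. The misprint is small, the correct value stands in the table in the same section, and a formal SAP is still to come.

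Much of this stands. The sized quantity is indeed planned; what is missing is a test of it against 0.70, or a statement that 0.70 is only a benchmark. The misprint alone would be minor. But a descriptive study should justify its N by precision, and 10.4 instead states a null and a power. A later SAP could name an analysis, but it would not correct 10.4.

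A reader might infer more than the documents support:

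- *That the sponsor will read a non-significant result as equivalence.* No passage says so.
- *That the study needs 107 injured wrists, or is badly underpowered, because 0.819 belongs to that row.* The protocol never proposes a test of 0.80 versus 0.90, and N = 34 follows correctly from the row that it does use.
- *That power falls simply because fewer than 31 injured wrists may be enrolled.* The exact test is discrete: its power is 0.807 with 31 injured wrists but 0.789, 0.770 and 0.750 with 32, 33 and 34. An average power would depend on a version of the test that the protocol does not name.

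**Conclusion.** The point holds and should be fixed, but it does not invalidate the design. N = 34 rests on a one-sample test of 0.70 versus 0.90 that no section plans, so the stated power describes neither the stated null nor the primary analysis. The correct power for the row used is 0.807 (size 0.048), not 0.819; this 1.2-point slip does not affect N. The main defect is the mismatch between the sizing and the stated hypothesis and analysis.

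The power figures assume a two-sided 0.05 level and exactly 31 injured wrists. The precision figures assume one result per wrist. Section 7.1.1 lists ten structures per wrist and the protocol does not define the unit of accuracy, so a per-structure analysis would give different intervals and ceilings, depending on clustering.

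**What to change.** **1. Section 10.4: choose one basis for N.**

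- *Default.* Delete the power of 0.819, and the no-difference null as the basis for N. Justify 34 by precision (exact 95% intervals, one result per wrist): accuracy 31/34, 76% to 98%; sensitivity 28/31, 74% to 98%; specificity 3/3, lower limit 29%, with about three uninjured wrists expected.
- *Alternative.* Add to 10.3.2 an exact two-sided one-sample test of NanoScope sensitivity against 0.70. Give its power as 0.807 with 31 reference-positive wrists (type I error 0.048). State that rejection shows only that sensitivity exceeds 0.70, not that the NanoScope matches conventional arthroscopy.

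Either way, say what 0.70 and 0.90 stand for and correct the type I error rate from 0.95 to 0.05. Do not add an average-power figure.

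**2. Section 10.3.2.** Report accuracy, sensitivity and specificity against conventional arthroscopy with Clopper-Pearson 95% intervals. If results are analysed per structure, use an interval that allows for clustering by wrist. State that the unpaired chi-squared of 10.3.1 is not used for the primary endpoint.

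**3. Section 10.2.** State the aim as estimating accuracy against conventional arthroscopy. Add that a non-significant difference will not be taken as evidence of no difference, and that any sole-use conclusion under 4.2.1 will be judged on the lower 95% confidence limit. Note that, with one result per wrist, this limit cannot exceed 88.8% for sensitivity (31/31) or 89.7% for accuracy (34/34).

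**Cost.** Wording only; N, endpoint, procedures and data collection stay as they are. The claim becomes narrower, and the stated power is lower or removed. The alternative adds a formal hypothesis that the protocol does not now have. If the sponsor also sets a numerical minimum for the lower limit, the adequacy of N becomes a design question. For example, a limit above 80% needs at least 32/34, which has probability 0.33 if true accuracy is 0.90.
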